10.6 Data Monitoring and Analysis

10.6.1 Study Monitoring Committee

No Data and Safety Monitoring Board oversight is planned for this study. The MTN SMC will conduct interim reviews of study progress, including rates of participant accrual, retention, completion of primary and main secondary endpoint assessments, study or lab issues. These reviews will take place approximately every 4-6 months, and as needed. At the time of these reviews, or at any other time, the SMC may recommend that the study proceed as designed, proceed with design modifications, or be discontinued.

10.6.2 Data Analysis

When the use of descriptive statistics to assess group characteristics or differences is required, the following methods will be used: for categorical variables, the number and percent in each category; for continuous variables, the mean, median, standard deviation, quartiles and range (minimum, maximum). Typically, within-group assessment of the difference between time-points will be analyzed using McNemar's test (for categorical response variables) or the paired t-test or Wilcoxon signed-ranks test (for continuous variables).

Primary Pharmacokinetics Analysis

To assess the impact of coitus (and semen) on the pharmacokinetics (PK) of tenofovir 1% gel in female genital tract secretions, vaginal/cervical tissue and rectal tract secretions, the concentration change in tenofovir and tenofovir diphosphate between the visits where the female participants dose with gel and engage in coitus vs. the visits where female participants dose with gel and do not engage in coitus will be assessed for drug concentration levels from vaginal/cervical tissue, blood, and rectal tract secretions within each group (Single Dose/BAT Cohort and Multiple Dose Cohort). The concentration change in tenofovir between these visits will also be assessed for drug concentration levels from CVL. For these analyses, the mean percentage change in drug concentration (DC) due to the impact of coitus will be calculated for each of the following PK assessments:

1. Tenofovir DC in CVL
2. Tenofovir DC on the cervical cytobrush
3. Tenofovir DC in vaginal tissue
4. Tenofovir DC in cervical tissue
5. Tenofovir-diphosphate DC in vaginal tissue
6. Tenofovir-diphosphate DC in cervical tissue
7. Tenofovir DC in blood
8. Tenofovir-diphosphate DC in blood
9. Tenofovir DC from rectal secretions

where the percentage change is defined for each couple as

$$\text{Percentage change} = (1 - ([\text{Gel}/\text{Coitus DC}] / [\text{Gel}/\text{No Coitus DC}]) \times 100\%$$

The difference in drug concentration levels at the visits where the female participants dose with gel and engage in coitus vs. the visits where female participants dose with gel and do not engage in coitus will be analyzed using the paired t-test or Wilcoxon signed-ranks test, as appropriate. In Group 1, for assessment of the BAT dosing regimen, DC from the visit where female participants perform BAT dosing with gel, coitus, and post-coitus gel will be compared to DC from the visit where female participants dose with gel (-1 hour) and do not engage in coitus. The BAT DC will also be compared to the visit where female participants dose with gel (-1 hour) and engage in coitus.

For each of the nine (9) assessments, the estimate of the mean percentage change along with the corresponding two-sided p-value and a 95% confidence interval will be presented. Significance level p-values will be adjusted for multiple comparisons using the FDR method.

In addition, change in amount (mass) of vaginal drug after dosing will also be assessed in CVL in similar fashion. As an explanatory variable, the screening semen sample from the male partner will be used to assess the typical semen biomarker value for each male participant so that the volume of ejaculate can be assessed using the CVL.

Primary Pharmacodynamic Analysis

In order to assess the impact of coitus (and semen) on pharmacodynamics (PD) of luminal drug by measuring the anti-HIV-1 activity in CVL samples, antiviral activity (percent inhibition) will be compared at various visits within each cohort. For Group 1, the difference in mean percent inhibition will be compared between:

1. No gel use with coitus vs. endogenous activity (baseline) (impact of coitus on endogenous activity)

For each group, and dose timing (-1 and -24 hours in Group 1 and -1 and -72 hours in Group 2), the difference in mean percent inhibition will be compared between:

2. Gel use alone vs. endogenous activity (baseline) (PD in absence of coitus)
3. Gel use with coitus vs. endogenous activity (baseline) (PD of product following coitus compared to baseline CVL activity)
4. Gel use alone vs. gel use with coitus (Difference in PD in the absence vs following coitus)
5. Gel use with coitus vs. no gel use with coitus (Group 1 only) (PD of product following coitus compared to post-coitus endogenous activity)

In Group 1, for assessment of the BAT dosing regimen, the difference in mean percent inhibition will be compared between:

1. Gel use, coitus, and post-coital gel use vs. endogenous activity (baseline) (PD of BAT compared to baseline CVL activity)
2. Gel use, coitus, and post-coital gel use vs. gel use (-1 hour) alone (Difference in PD of BAT compared to absence of coitus and post-coital gel)
3. Gel use, coitus, and post-coital gel use vs. gel use (-1 hour) with coitus (Difference in PD of BAT compared to absence of post-coital gel)
4. Gel use, coitus, and post-coital gel use vs. no gel use with coitus (PD of BAT compared to post-coitus endogenous activity)

Differences will be assessed with the use of the paired t-test or Wilcoxon signed-ranks test, as appropriate.

Secondary Acceptability Analysis

Descriptive statistics will be used to summarize behavioral, adherence, and acceptability data. Behavioral characteristics will be described in terms of the proportion of couples reporting sexual behaviors and practices prohibited during study participation. The adherence to product use will be described among couples in the Multiple Dose Cohort (Group 2) only, and will include assessment of the number and percentage of expected daily doses taken. The perceived acceptability of study procedures and use of the product will be described by the proportion of couples indicating that the product or procedures were found to be acceptable. The proportion of couples willing to take part in a trial of similar design in the future will be calculated. No formal testing will be performed.

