2.5 Clinical Studies

2.5.1 Clinical Studies of Tenofovir

Pharmacokinetics

A Phase 1 Safety and Acceptability Study of the Vaginal Microbicide Agent PMPA Gel, also known as HPTN 050, a study of tenofovir vaginal gel with published data, examined the PK of tenofovir gel.¹⁶ Eighty-four (60 HIV negative and 24 HIV positive) women applied either 0.3% or tenofovir 1% gel once or twice daily for 14 days. Systemic absorption was limited (maximum serum levels 3.1-25.8 ng/mL).

A randomized trial to assess anti-HIV activity and soluble mucosal immunity following application of tenofovir gel also provided data on the PK of tenofovir gel.¹⁷ With daily dosing, 12 participants in the tenofovir arm of the study yielded mean (SD) CVL tenofovir levels at Days 3, 7, and 14 of 9.5×10^3 (11.2×10^3), 24.7×10^3 (26.4×10^3), and 16.0×10^3 (20.5×10^3) ng/mL, respectively.

A study of the pharmacokinetics of tenofovir gel was conducted among 49 sexually abstinent women in the USA and Dominican Republic (CONRAD A04-095, IND 73,382).¹⁸ The following are results from a subset (n=21) who completed the single-dose phase. Following an intravaginal dose (4 g) of tenofovir gel, blood samples were obtained at 0.5, 1, 2, 4, 6, 8, and 24 hr(s) from all participants. Participants were randomized to one of seven time-points [0.5, 1, 2, 4, 6, 8, and 24 hr(s)] for vaginal fluid collection and vaginal biopsies. Total tenofovir (TFV) was measured in blood plasma, fluid, and biopsies. Most blood plasma TFV concentrations were below 5 ng/mL. Four had higher values (up to 19.5 ng/mL), which were not sustained. Vaginal fluid concentrations were high, generally $1.5\text{-}5.0 \times 10^6$ ng/mL through 8 hrs and $4.5\text{-}47.1 \times 10^4$ ng/mL at 24 hrs. The mean concentration in vaginal tissue at 0.5, 1, 2, 4, 6, 8 and 24 hr(s) were 275×10^3 , 450×10^3 , 186×10^3 , 89×10^3 , 69×10^3 , 24×10^3 and 15×10^3 ng/g of tissue, respectively, (LLOQ=1 ng/mL) with a peak at 1-4 hrs. Vaginal fluid elimination appeared linear. Tissue elimination appeared to follow a multi-compartment model. Total TFV was detectable in vaginal tissue and fluid up to 24 hrs post single-dose exposure.

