No statistically significant differences were seen between those receiving active and placebo gels in complete blood count (CBC), liver function tests, or renal function tests. Among women using study gel, no participants had pelvic exam findings involving generalized erythema or severe edema or deep epithelial disruption at any follow-up visit during the study. At the Week 24 Visit, no participants had exam findings suggestive of vaginitis, cervicitis, superficial disruption, disrupted blood vessels, or intermenstrual bleeding. Adherence to study gel was high, and was supported by PK data. 79% of women reporting gel use in past 12 hours had low but detectable plasma tenofovir supporting self-reported adherence data. Daily and coital use was highly acceptable to women. These data suggest a favorable safety and acceptability profile of tenofovir gel.²¹

In MTN-002, the first microbicide trial to be conducted during pregnancy, 16 women received a single vaginal dose of tenofovir 1% gel prior to elective cesarean section. Blood, amniotic fluid, cord blood, endometrial tissue, and placental tissue were collected from participants.²² Plasma tenofovir levels were compared to historical controls. Study results demonstrated that tenofovir levels following a single vaginal dose of tenofovir 1% gel in pregnant women were similar to those found in non-pregnant women, and that levels were up to 50 – 100 times less compared to standard oral dosing. Tenofovir was detectable in the fetal compartment, with low overall cord levels (approximately 40 times less than observed in oral dosing), but with a similar cord blood: maternal ratio. Overall, findings suggest that tenofovir is safe for use in term pregnancy and warrants additional investigation of repeat dosing during pregnancy.

RMP-02/MTN-006 was a Phase 1 study designed to evaluate the safety and early pharmacokinetic profile of 1% vaginally-formulated tenofovir gel, applied rectally, during a single exposure followed by once-daily dosing for 7 days, as compared to a single oral dose. Rectal dosing with the vaginal formulation of tenofovir 1% gel was found to be neither entirely safe nor fully acceptable. A regimen of 7 rectally applied daily doses of tenofovir 1% gel resulted in significant inhibition of ex vivo HIV challenge of biopsy tissue, whereas neither single dosing of oral (TDF) nor single rectal (TFV) dosing resulted in significant protection of tissue against ex vivo viral challenge.²³

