Administration of tenofovir gel intravaginally at 0.3% and 1% concentrations in the HPTN 050 Phase1 study resulted in minimal local irritation and little or no systemic AEs were identified. Although 92% of participants reported at least 1 AE, 87% of those reported AEs were mild, and 70% of the AEs were limited to the genitourinary tract. Four severe AEs were reported, with only one, lower abdominal pain, thought to be product-related. The risks associated with tenofovir gel are believed to be less than those identified for systemic use. Some of the possible side effects of the study gel are dryness, itching, burning, or pain in the genital area.

In the HPTN 050 Phase 1 study of tenofovir gel, serum PK analysis in a subset of participants demonstrated that there is no clinically significant systemic toxicity. Fourteen of 25 women with PK results had low, but detectable, serum tenofovir levels. Given that Phase 1 data demonstrate measurable plasma concentrations of tenofovir in some participants, participants with hepatitis B infection might be at risk for development of tenofovir-resistant hepatitis B. However, participants with known hepatitis B infection will not be eligible for enrollment. It is not known what effect tenofovir gel could have on the HIV virus or HIV disease progression in HIV-infected participants or their partners. There is a theoretical risk that tenofovir absorbed systemically from oral TDF or vaginal tenofovir gel could result in mutations of the HIV virus in participants who become infected with HIV during the study, or their partner, if the partner is infected with HIV. Limited resistance data from HPTN 050 show no new resistance mutations in plasma or cervicovaginal lavage specimens after 14 days of tenofovir gel use. No participant had high level tenofovir mutations (e.g., K65R).

In a male tolerance study of tenofovir 1% gel, there were few genital findings observed after product use and all findings were classified as mild, small in size and required no treatment.²⁶ The most common side effects include mild pain (burning, irritation, discomfort) and itching. All reported urogenital symptoms were felt to be mild.

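### The mean per-couple percentage change is a poor fixed estimate for blood: it has no finite value when the no-coitus level is undetectable, and its bias depends on how non-detects are handled

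*Protocol*

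**What the plan says.** Under the primary pharmacokinetics analysis, section 10.6.2 states that "the mean percentage change in drug concentration (DC) due to the impact of coitus will be calculated for each of the following PK assessments". Nine assessments follow. Number 7 is tenofovir in blood and number 8 is "Tenofovir-diphosphate DC in blood". The formula applies to all nine ("where the percentage change is defined for each couple as"): one minus the gel-with-coitus level over the gel-without-coitus level, times 100%. For every assessment, "the estimate of the mean percentage change along with the corresponding two-sided p-value and a 95% confidence interval will be presented", with FDR adjustment of the p-values. The test itself is worded on the difference in levels, which "will be analyzed using the paired t-test or Wilcoxon signed-ranks test, as appropriate".

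Elsewhere the protocol describes how often tenofovir is measurable in blood after vaginal gel:
- Section 13.4.1, on HPTN 050: "Fourteen of 25 women with PK results had low, but detectable, serum tenofovir levels".
- Section 2.5.1, on HPTN 059: "79% of women reporting gel use in past 12 hours had low but detectable plasma tenofovir".
- Section 2.5.1, on the single-dose study CONRAD A04-095: "Most blood plasma TFV concentrations were below 5 ng/mL".

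Blood is a listed primary PK endpoint (sections 4.2 and 10.2.1). The primary objective in section 3.1 names genital secretions, tissue and rectal secretions, but not blood.

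**The concern.** A ratio needs a denominator that can be measured. The protocol's own background says blood tenofovir after gel is often undetectable, yet blood gets the same ratio as cervicovaginal lavage, where levels are high. If the no-coitus value is recorded as zero, the couple's percentage change is 0/0 or x/0. Some handling rule must then rescue it, and the rule chosen may drive the answer. The reported coital effect on blood levels, with its interval, could then owe more to the treatment of non-detects than to coitus.

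**Working it through.** **Inputs from the protocol.**
- 20 evaluable couples per group; 25% called biologically important; SD of the percentage change 37.5% (section 10.4.1).
- Detectable blood tenofovir: 79% (HPTN 059) and 14 of 25 (HPTN 050).
- CVs of 1.2 and 1.1 for lavage levels (section 10.4.1). No CV is given for blood.

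**The plan's own figure.** Two-sided paired t-test, alpha 0.05 (assumed, as no number is stated), n = 20, 25%/37.5%: noncentral-t power is 0.807, as in Table 18.

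**Couples without a finite ratio.** Undetectable share: 1 − 0.79 = 0.21, and 11/25 = 0.44. Of 20 couples, 0.21 × 20 = 4.2 and 0.44 × 20 = 8.8, so about 4 to 9. If only the post-coital value is undetectable and is set to zero, the ratio is defined and equals a 100% loss. As an illustration only, since the 37.5% was derived for lavage: the same power formula gives 0.70 with 16 couples and 0.51 with 11.

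**Mean under no coital effect.** Assumptions: lognormal levels with the same distribution at both visits; the same LLOQ, cutting off 21% or 44%; log SD 0.8–1.0; within-woman log-scale correlation 0.3–0.6. For orientation, the lavage CVs give log SDs of √ln(1 + 1.1²) = 0.89 and √ln(1 + 1.2²) = 0.94. Simulated with 4 million pairs per setting. Entries are the mean percentage change; positive is an apparent loss and the true value is 0.

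| Log SD | Correlation | Undetectable | Drop if no-coitus value undetectable; post-coital non-detects = 0 | LLOQ/2 for all non-detects | Both values detectable | Complete data |
|---|---|---|---|---|---|---|
| 0.8 | 0.3 | 21% | −12 | −67 | −36 | −57 |
| 0.8 | 0.3 | 44% | +18 | −56 | −27 | −57 |
| 0.8 | 0.6 | 21% | −6 | −37 | −22 | −29 |
| 0.8 | 0.6 | 44% | +12 | −33 | −19 | −29 |
| 1.0 | 0.3 | 21% | −33 | −107 | −61 | −101 |
| 1.0 | 0.3 | 44% | +6 | −82 | −45 | −101 |
| 1.0 | 0.6 | 21% | −19 | −55 | −37 | −49 |
| 1.0 | 0.6 | 44% | +3 | −46 | −31 | −49 |

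The complete-data column is exact: 100 × (1 − exp[SD² × (1 − correlation)]). For SD 0.8 and correlation 0.3 this is 100 × (1 − exp 0.448) = −57. So part of the apparent gain comes from averaging ratios and would occur with no non-detects at all.

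Two results stand out. None of the three rules gives a reliably unbiased mean. And in a single null setting (log SD 0.8, correlation 0.3, 44% undetectable) the answer is +18%, −56% or −27%, depending only on the rule.

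**The case against.** Several points on the other side are sound.

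- **Missing LLOQ rule.** Handling of values below quantification commonly sits in the SAP, which is not shown. Its absence from the protocol is no fault, and any substitution rule gives every couple a value. That stands. But the protocol has already fixed the quantity to be averaged, and the table shows that the usual rules make its mean computable without making it trustworthy.
- **Spurious loss.** A reader might infer that the remaining couples must show a false coital loss. Under one rule (drop on the denominator, keep post-coital non-detects as zero) the null median is indeed a loss of 11% to 46%. But the protocol reports the mean and states no such rule. With LLOQ/2 or both-detectable pairs the null median is 0, and the mean points to a gain. No general direction can be claimed.
- **The test.** It is worded on differences in levels, which remain computable with zeros and lose no couple. That stands, so the p-value is not undefined.
- **The rates.** The 44% is serum after 0.3% or 1% gel, once or twice daily (sections 2.5.1 and 13.4.1). The 21% is self-reported use within 12 hours. Neither concerns the diphosphate. Levels under 5 ng/mL are not thereby unquantifiable: the only LLOQ given, 1 ng/mL, appears with the tissue results. All of this stands. Rates at the −24 h and −72 h visits are unknown and could be higher.
- **Reach.** Evaluability (section 10.5) requires lavage and tissue levels only, and the sample size rests on lavage data. A reader might infer that the trial loses evaluable couples or planned power; it does not.

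**Conclusion.** The concern holds in a limited form. For assessments 7 and 8 the protocol fixes a mean ratio that has no finite value when the no-coitus level is taken as zero. Its own background suggests this could affect a sizeable share of women, about 4 to 9 of 20 if the cited tenofovir rates carried over.

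Under no effect, the mean is biased by amounts that can exceed the 25% called important, with sign and size set by the handling of non-detects. These sizes rest on lognormal levels and on the assumed SDs and correlations, because the protocol gives no variability for blood. What is affected is the stated estimate and its confidence interval. The test on differences, the evaluability rule and the sample size are not. The wording should be changed, but the design is not at risk.

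**What to change.** In section 10.6.2, replace the mean per-couple ratio for assessments 7 and 8, and for any other matrix and dose timing where unquantifiable values occur. Use a paired analysis of log concentration that keeps every couple and treats values below the LLOQ as left-censored, for example a censored mixed model. Report a geometric mean ratio with 95% CI; 100 × (1 − ratio) keeps the familiar percentage scale. A paired Prentice-Wilcoxon test is the rank-based alternative. Alongside it, give the proportion quantifiable with and without coitus, compared by McNemar's test, which 10.6.2 already names for categorical responses.

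The cost is protocol or SAP wording and somewhat more analysis, with no new samples, visits or couples. The estimate is less simple to present and leans on the lognormal assumption when many values are censored.

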10.4 Sample Size and Power Calculations

The sample size of 40 evaluable couples, with 20 couples in each group (Single Dose /BAT Cohort and Multiple Dose Cohort), was determined with respect to the primary PK endpoints. Details are provided in the section below. Given this sample size, power calculations are also provided for the PD primary endpoint.

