10.4.1 Pharmacokinetic Endpoints

Sample size/power formulas for a one-sample, paired t-test, can be used to compute sample size/power. For the primary PK endpoint to assess the impact of coitus on the PK of tenofovir following a single dose and BAT regimen (Group 1), and separately if indicated, following seven daily doses (Group 2), we use data from two studies:

- 1) a 14-day tenofovir gel study in which CVL TFV levels and anti-HIV-1 activity were measured on Days 3 and 7,¹⁷ and
- 2) a post-coital study by Keller, et al.⁵ which addressed the impact of coitus on the PK of PRO 2000 Gel following a single dose of gel.

From these studies, we estimate the standard deviation of CVL tenofovir data after daily dosing at Days 3 and 7, and the standard deviation for the percentage difference in drug concentration (DC) levels between gel use alone and gel use prior to coitus. We make the assumption that the standard deviation for this percentage difference will be similar for tenofovir 1% gel as it was for PRO 2000 Gel. We also assume that the standard deviation will be similar for the percentage difference due to coitus following seven daily doses as it was for coitus following a single dose.

From the tenofovir 14-day study, we estimated the coefficient of variation (CV) of the gel-only DC levels from CVL at Days 3 and 7 to be 1.2 and 1.1, respectively. From the PRO 2000 Gel study we estimated the mean (SD) percentage change in CVL drug concentration due to the impact of coitus ($1 - ([\text{gel and sex DC}] / [\text{gel-only DC}]) \times 100\%$ for each couple). The mean percentage change was 68% and the standard deviation was 31% (CV of $0.31/0.68=0.5$). The gel/sex and gel-only PRO 2000 DC levels yielded CVs of 1.1 and 0.9, respectively. The tenofovir 14-day study produced mean tenofovir DC levels on the same order of magnitude (ng/mL) as seen with the PRO 2000 DC levels in the PRO 2000 post-coital study. For the MTN-011 study, we assume a conservative CV of 1.5 for the mean percentage change due to the impact of coitus. It is estimated that a 25% difference in drug concentration levels due to coitus would be biologically important to be able to detect. Thus, a CV of 1.5 translates to a standard deviation of 37.5%, and with a sample size of 20 couples, this study is designed with 80% power to detect at least a 25% difference in drug concentration levels due to coitus.

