Based on a one-sample, paired t-test, the table below summarizes the power available to detect various percentage differences in drug concentration levels due to coitus for a sample size of 20 couples. The table also provides this information for various estimates of the standard deviation (Sigma) in the case that our assumptions are not met.

Table 18: Power for Minimum Detectable Differences in Drug Concentration Levels for Within Group Comparisons of Gel Use vs. Gel Use Prior to Coitus (N=20)

Minimum detectable difference in drug concentration levels	Sigma (CV)				
	0.25 (1.0)	0.3125 (1.25)	0.375 (1.5)	0.4375 (1.75)	0.5 (2.0)
5%	0.136	0.104	0.088	0.077	0.071
10%	0.397	0.274	0.205	0.163	0.136
15%	0.721	0.531	0.397	0.308	0.247
20%	0.924	0.775	0.619	0.492	0.397
25%	0.989	0.924	0.807	0.679	0.565
30%	>0.999	0.982	0.924	0.829	0.721
35%	>0.999	0.997	0.977	0.924	0.844
40%	>0.999	>0.999	0.995	0.972	0.924
45%	>0.999	>0.999	>0.999	0.992	0.968
50%	>0.999	>0.999	>0.999	0.998	0.989

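### The 80% PK power in Protocol 10.4.1 is for one unadjusted test, while 10.6.2 adjusts nine primary PK p-values by FDR; assuming Benjamini-Hochberg at 5%, per-assessment power is about 46–77%

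*Protocol*

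**What the plan says.** Protocol 10.4 plans "The sample size of 40 evaluable couples, with 20 couples in each group" and says that this number "was determined with respect to the primary PK endpoints".

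Section 10.4.1 sets the target: "It is estimated that a 25% difference in drug concentration levels due to coitus would be biologically important to be able to detect". It takes a CV of 1.5, hence an SD of 37.5%, and concludes that "with a sample size of 20 couples, this study is designed with 80% power to detect at least a 25% difference in drug concentration levels". Table 18 is introduced with "Based on a one-sample, paired t-test, the table below summarizes the power available", and its cell for 25% and Sigma 0.375 is 0.807. Section 10.4.1 states no alpha and does not mention multiplicity.

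Section 10.6.2 (Primary Pharmacokinetics Analysis) numbers nine PK assessments, with tenofovir in CVL first. It then prescribes what is reported: "For each of the nine (9) assessments, the estimate of the mean percentage change along with the corresponding two-sided p-value". Each estimate also gets a 95% interval. The adjustment rule comes straight after: "Significance level p-values will be adjusted for multiple comparisons using the FDR method".

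**The concern.** The power claim and the analysis rule concern the same primary comparisons but use different significance levels. The power is worked out as if each comparison stood alone at 0.05. Significance is to be read from p-values adjusted across nine assessments, which puts a stricter hurdle in front of each one unless every assessment is significant together.

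The 80% is the protocol's only PK power statement at its chosen effect size, and it is the justification for 20 couples per group. The study hypotheses (2.6.1 and 10.3) are that coitus has no impact. A non-significant adjusted p-value would therefore tend to be read as agreeing with the hypothesis, and a reader would judge the weight of that null by the printed 80%. If the real figure is lower, the null looks firmer than it is.

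**Working it through.** **Inputs from the protocol.** n = 20 couples per group (10.4); difference 25%, SD 1.5 × 25% = 37.5%, paired t-test (10.4.1); two-sided p-values, 95% confidence intervals, nine assessments, FDR adjustment (10.6.2).

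**Step 1: reproduce the plan's figure.** Standardised effect 0.25/0.375 = 0.667; noncentrality 0.667 × √20 = 2.98; df = 19. At two-sided 0.05 the critical value is t = 2.093, and the noncentral t distribution gives power 0.807, as printed. All cells of Table 18 reproduce on this basis. One-sided 0.05 would give 0.890, and a two-sided normal approximation 0.846. So the table uses one test at unadjusted two-sided 0.05.

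**Step 2: exact floor under FDR.** Benjamini-Hochberg sorts the p-values and compares the i-th smallest with q × i/9. Its strictest step, with q = 0.05, is 0.05/9 = 0.0056. The critical value becomes 3.127 and the power 0.464. The difference detectable with 80% power at SD 37.5% is 24.8% at alpha 0.05 and 33.8% at 0.05/9.

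**Step 3: simulate the full procedure.** The protocol does not say how many assessments coitus would affect or how they correlate, so both are varied. Each affected assessment is given the plan's 25% and 37.5%; the others have no effect. Per-assessment power, with a common correlation of 0 to 0.6 (20,000 to 40,000 replicates per scenario):

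| Assessments truly affected | FDR level 5% | FDR level 10% |
|---|---|---|
| 1 | 46–48% | 59–60% |
| 2 | 53–54% | 66–67% |
| 3 | 58–59% | 71–73% |
| 5 | 65–68% | 78–80% |
| 9 | 74–77% | 84–88% |

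At correlation 0.8 the first and last rows are 46% and 73% at the 5% level, and 58% and 84% at the 10% level.

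**Step 4: other readings of the rule.** Benjamini-Yekutieli at 5%, independent assessments: 32% with one affected, 57% with all nine. Benjamini-Hochberg at 5% over 18 tests (nine assessments at both dose timings of a group): about 36–37% with one affected.

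**The case against.** **Table 18 contains no error of calculation.** This stands. Each cell is right for what the table's introduction describes. The fault is that the basis is not labelled as unadjusted and does not match 10.6.2.

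**The shortfall rests on inputs the protocol does not give.** This also stands in part. The procedure, level and family may be fixed in a statistical analysis plan that is not at hand. At a 10% level the shortfall disappears if all nine assessments are affected, and about 80% is reached with five affected and uncorrelated. The 95% intervals make 5% the natural reading, but 10.6.2 does not say so. The mismatch itself needs no outside detail, because the protocol prints both the 80% and the adjustment.

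**The loss matters only near 25%.** Section 10.4.1 reports a mean loss of 68% in the PRO 2000 post-coital study. At alpha 0.05/9 and SD 37.5%, power is already 83% for a 35% loss and 93% for 40%. That is true and limits the practical effect, but the 80% claim is made at 25%, the difference the protocol calls important.

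**Some affected assessment would probably be found.** With all nine affected, the chance of at least one significant result is 81% to over 99%, for correlation 0.8 down to 0. Table 18 gives power per comparison, however, so per-assessment power is the like-for-like figure.

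**A reader might infer** that the protocol expects an effect on CVL alone, so that a true 25% loss would be missed more often than not. The documents do not support this. Section 2.6.2 speaks of dilution and displacement in CVL and cytobrush, rectal sponge, and vaginal and cervical tissue. Once two assessments are affected, power at the 5% level is above one half.

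**A reader might also infer** a formal success criterion. Section 10.6.2 says only that estimates, p-values and intervals will be presented, and no go/no-go decision hangs on them.

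**Conclusion.** The point holds as a mismatch between a stated power and a stated analysis rule. The 80% is correct for one paired t-test at unadjusted two-sided 0.05, but it is not the power under the FDR adjustment as written. Assuming Benjamini-Hochberg at 5% over nine assessments, and the plan's 25% and 37.5% for every affected assessment, per-assessment power runs from about 46–48% (one affected) to 74–77% (all nine). The 80%-power detectable difference is about 34% in the one-affected case. No 5% scenario tried reached 80%. At an FDR level of 10% the range is about 58–88%.

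Two limits apply. The 25% target and the SD rest on CVL data, so carrying them to tissue, blood and rectal measures is an assumption. And the finding does not show that 20 couples are too few for the study's purpose; it shows only that the printed power describes a different test.

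**What to change.** In 10.4.1, label the 80% and Table 18 as power for a single comparison at unadjusted two-sided 0.05. Beside them, state the per-assessment power under the FDR rule, naming the procedure and level assumed. With Benjamini-Hochberg at 5% over nine assessments, the added text would give about 46–48% if one assessment is affected, rising to 74–77% if all nine are, with a detectable difference of about 34% in the one-affected case.

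No couples, samples or assays are added. It is not necessary to exempt CVL from the adjustment to make the table fit. Section 10.5 names CVL and the vaginal/cervical biopsies together as the primary PK endpoints, so ranking CVL first would be a separate trade-off that loosens the stated multiplicity control. The only cost is a less favourable stated power.
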